Myelodysplastic syndrome (MDS) and acute myeloid leukemia (AML) are considered adverse events of special interest (AESIs), as these events have been observed in patients exposed to cytotoxic chemotherapy (eg, platinum and anthracyclines) used for treatment of ovarian cancer as well as with PARP inhibitors, including rucaparib. Patients in rucaparib clinical studies diagnosed with MDS or AML had significant confounding risk factors including prior cytotoxic chemotherapy, as well as a deleterious BRCA mutation.^{39,40} Based on these confounding factors, there is insufficient scientific evidence to conclude that MDS and AML are causally related to rucaparib. More information on AESIs for rucaparib is provided in the rucaparib IB.

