- In addition, if anemia CTCAE Grade ≥ 3 persists for > 14 consecutive days, or a dependence upon blood transfusion occurs, then weekly complete blood counts should be performed until resolution of the event.
- If, after 42 days of interruption of rucaparib, the anemia has not improved to CTCAE Grade ≤ 1 then the patient should be referred to a hematologist and analysis of the bone marrow with cytogenetic studies are recommended according to standard hematologic practice.
- The bone marrow analysis should include a bone marrow aspirate (for cellular morphology, cytogenetic analysis, and flow cytometry) and a core biopsy (for bone marrow cellularity).

5.4.1.3 Management of Rucaparib Treatment-Emergent ALT/AST Elevations:

- Grade 4 ALT/AST elevations: hold rucaparib until values have improved to Grade 2 or better, then resume rucaparib with a dose reduction. Monitor liver function tests weekly for 3 weeks after rucaparib has been restarted.
- Grade 3 ALT/AST elevations, in the absence of other signs of liver dysfunction, should be managed as follows:
 - Monitor liver function tests weekly until improvement to \leq Grade 2.
 - Continuation of rucaparib with elevation of ALT/AST up to Grade 3 is permitted provided bilirubin is $<$ ULN and alkaline phosphatase is $< 3 \times$ ULN.
 - If patient has Grade 3 ALT/AST and continues on rucaparib, and levels do not decline within 2 weeks or they continue to rise, treatment interruption and resolution to \leq Grade 2 will be required before rucaparib can be resumed, either at the current dose or at a reduced dose.

Drug-induced liver injury (DILI) is described in the US FDA Guidance for Industry, Drug-Induced Liver Injury: Premarketing Clinical Evaluation⁴² and should be referenced when managing treatment-emergent ALT/AST elevations.

Rucaparib treatment must be interrupted if biochemical criteria for suspected DILI are met, according to presence of the following laboratory abnormalities:

ALT or AST > 3 x ULN
and
Bilirubin > 2 x ULN

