7.5.3 Long-term Follow-up

Patients who complete a 28-day Follow-up Visit after the last dose of rucaparib will continue in long-term follow-up as described below.

- If applicable, tumor assessment (using the same methodology as was used at initial study screening [eg, CT scan or MRI scan if required by local authorities]) when the reason for treatment discontinuation was other than death or disease progression based on radiologic assessment and it has been ≥ 8 weeks since last scan or disease progression was noted on the last scan. Tumor assessment should continue to be performed at the end of every 8 calendar weeks (± 7 days) relative to Cycle 1 Day 1 up to 18 months, then every 12 calendar weeks (± 7 days), until confirmed radiologic disease progression by RECIST v1.1 criteria as assessed by the investigator, loss to follow-up, withdrawal, death, initiation of subsequent treatment, or study closure.
- All patients discontinued from treatment, regardless of reason, will be followed and information collected for subsequent treatments and survival every 12 weeks from last dose of rucaparib until death, loss to follow-up, withdrawal of consent from study, or closure of the study. Follow-up can be performed via the telephone and can be completed to coincide with scheduled tumor assessments.
- SAEs related to rucaparib and all AESIs, irrespective of causality, are to be reported as specified in [Section 8.9](#).

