7.6.4 Safety Evaluations

7.6.4.1 Adverse Event Assessment

The investigator has the responsibility for assessing the safety of the patients and for compliance with the protocol to ensure study integrity. During the screening period, unless otherwise required by local regulations, SAEs which are related to protocol-mandated assessments will be reported. Once enrolled and rucaparib is administered, patients will be monitored for all AEs/SAEs/AESIs during study participation and until 28 days after the last dose of rucaparib. After the 28-day window, only treatment-related SAEs and all AESIs, irrespective of causality, need to be reported. Any ongoing SAEs, AESIs, or treatment-related Grade 3/4 AEs will be followed until resolution or stabilization or until loss to follow-up. AEs and laboratory abnormalities will be graded according to the NCI CTCAE grading system (Version 4.03 or later) and recorded on the eCRF.

Complete details for monitoring AEs, including the definition of drug-related AEs, are provided in [Section 8](#).

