8.6 Pregnancy or Drug Exposure during Pregnancy

If a patient becomes pregnant during the course of the study, rucaparib dosing should be held immediately.

Pregnancy is not considered to be an AE or SAE; however, all pregnancies occurring during study participation or within 6 months of last dosing must be reported to the sponsor using the Pregnancy Report Form within the same timelines as for an SAE.

All pregnancies should be followed through to outcome. Once the outcome of a pregnancy is known, the Pregnancy Outcome Report Form should be completed and submitted to the sponsor.

AEs, SAEs, or AESIs that occur during pregnancy will be assessed and processed according to the AE or SAE/ AESI processes using the appropriate AE or SAE/ AESI forms.

8.7 Recording of Adverse Events, Serious Adverse Events, and Adverse Events of Special Interest

Events that occur after signing of informed consent, but prior to initiation of rucaparib, unless due to a protocol-mandated procedure, will be recorded on the Medical History eCRF. Any event related to a protocol-mandated procedure should be reported during the screening period. Any AE that occurs after first dose of rucaparib through 28 days after receiving the last dose of rucaparib will be recorded on the AE eCRF. After the 28-day reporting window after discontinuation of rucaparib treatment, only SAEs assessed as related to rucaparib and all AESIs, irrespective of causality, need to be reported. Information on the follow-up of AEs, SAEs, and AESIs is provided in [Section 8.8](#).

In order to avoid vague, ambiguous, or colloquial expressions, the AE should be recorded in standard medical terminology rather than the patient's own words. Whenever possible, the investigator should combine signs and symptoms that constitute a single disease entity or syndrome into a final diagnosis, if appropriate. For example, fever, cough, and shortness of breath may be reported as pneumonia, if that is a reasonable diagnosis.

Each AE is to be evaluated for **causal relationship**, severity, and seriousness to the investigational drug. The action taken and the outcome must also be recorded.

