9.7.1 Adverse Events

Adverse events will be classified using the Medical Dictionary for Regulatory Activities (MedDRA) classification system. The severity of the toxicities will be graded according to the NCI CTCAE Version 4.03 or later. Only treatment-emergent adverse events (TEAEs) will be collected: TEAEs are defined as AEs with onset date on or after the date of first dose of rucaparib until the date of the last rucaparib dose plus 28 days.

The number and percentage of patients who experienced TEAEs for each System Organ Class (SOC) and Preferred Term (PT) will be presented. Multiple instances of the TEAE in each SOC and multiple occurrences of the same PT are counted only once per patient. The number and percentage of patients with at least 1 TEAE will also be summarized.

Separate tables will be presented as follows:

- All TEAEs;
- TEAEs by CTCAE grade;
- Grade 3 or higher TEAEs;
- Treatment-related TEAEs;
- Serious TEAEs;

- TEAEs with an outcome of death;
- TEAEs leading to discontinuation of study medication;
- TEAEs resulting in interruption/delay of study medication; and
- TEAEs resulting in dose reduction of study medication.

The incidence of TEAEs will be summarized by relationship to rucaparib according to the following categories: “treatment-related,” or “not treatment-related.” If a patient experiences multiple occurrences of the same AE with different relationship categories, the patient will be counted once, as a relationship category of treatment-related.

If a patient experiences multiple occurrences of the same AE with different toxicity grades, the patient will be counted once for the maximum (most severe) toxicity grade. AEs with a missing toxicity grade will be presented in the summary table with a toxicity grade of “Missing.” For each toxicity grade, the number and percentage of patients with at least 1 TEAE of the given grade will be summarized.

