11.1 Adverse Events

Adverse events will be classified using the MedDRA classification system. The severity of the toxicities will be graded according to the National Cancer Institute (NCI) Common Terminology Criteria for Adverse Events (CTCAE) whenever possible. Treatment-emergent adverse events (TEAEs) are defined as AEs with onset date on or after the date of first dose of study medication until the date of the last study medication dose plus 28 days. Adverse events will be considered treatment-emergent if all or part of the date of onset of the AE is missing and it cannot be determined if the AE meets the definition for treatment-emergent.

The number and percentage of patients who experienced TEAEs for each system organ class and preferred term will be presented. Multiple instances of the TEAE in each system organ class and multiple occurrences of the same preferred term are counted only once per patient. The number and percentage of patients with at least one TEAE will also be summarized.

The incidence of TEAEs will also be summarized by relationship to study drug according to the following categories: “treatment-related,” or “not treatment-related”. If a patient

experiences multiple occurrences of the same AE with different relationship categories, the patient will be counted once, as a relationship category of treatment-related.

If a patient experiences multiple occurrences of the same AE with different toxicity grades, the patient will be counted once for the maximum (most severe) toxicity grade. AEs with a missing toxicity grade will be presented in the summary table with a toxicity grade of "Missing." For each toxicity grade, the number and percentage of patients with at least one TEAE of the given grade will be summarized.

The time to the first TEAE and first treatment-related TEAE that results in a dose reduction, delay, interruption, or discontinuation of study drug is defined as 1+ the number of days from the first dose of study drug to the start of the first TEAE.

Separate tables will be presented including but not limited to:

- All TEAEs;
- TEAEs by CTCAE grade;
- Grade 3 or greater TEAEs;
- Treatment-related TEAEs, overall and by categories: CTCAE grade, grade 3 or greater, resulting in dose reduction, resulting in dose interruption, resulting in dose discontinuation, outcome of death;
- Serious TEAEs, overall and by categories: age, sex, and treatment-relatedness;
- TEAEs with an outcome of death;

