- TEAEs leading to discontinuation of study medication;
- TEAEs resulting in interruption of study medication; and
- TEAEs resulting in reduction, delay, or interruption of study medication.
- Time to the first TEAE that results in a reduction, delay, interruption, or discontinuation of study drug.
- Time to the first treatment-related TEAE that results in a reduction, delay, interruption, or discontinuation of study drug.

Non-TEAEs (pre-treatment and post-treatment) will be presented in the by-patient data listings for the safety population.

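### MDS/AML starting more than 28 days after the last dose must be reported, but no adverse event table named in SAP 11.1 would count it

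*SAP*

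**What the plan says.** **Reporting.** Protocol 1.3.2.2.3 classes MDS and AML as AESIs, and Protocol 8.3 refers to the Investigator's Brochure for the current AESI list. After the 28-day window, Protocol 7.6.4.1 says "only treatment-related SAEs and all AESIs, irrespective of causality, need to be reported". Protocol 8.7 repeats the rule ("only SAEs assessed as related to rucaparib and all AESIs, irrespective of causality, need to be reported"), as do Protocol 8.8 and 8.9. Protocol 7.5.3 carries it into long-term follow-up: "SAEs related to rucaparib and all AESIs, irrespective of causality, are to be reported as specified in" Protocol 8.9.

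**Tabulation.** SAP 11.1 runs the treatment-emergent window from first dose "until the date of the last study medication dose plus 28 days". The tables it names are all tables of treatment-emergent events (TEAEs). For the rest it says: "Non-TEAEs (pre-treatment and post-treatment) will be presented in the by-patient data listings for the safety population". The SAP text supplied does not mention AESIs, MDS or AML. The table list in Protocol 9.7.1 has no AESI table either.

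**A conflicting statement.** Protocol 9.7.1 says "Only treatment-emergent adverse events (TEAEs) will be collected", which does not fit the rules for later AESIs.

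**The concern.** MDS and AML can appear after treatment has stopped, and the protocol recognizes this by keeping AESI reporting open with no causality filter. The analysis plan does not follow through. It closes the tabulated window 28 days after the last dose and sends later events to by-patient listings.

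One of the trial's safety endpoints is the incidence of adverse events, and a listing does not give an incidence. A reader who takes MDS/AML incidence from the named tables would get a figure limited to the treatment-emergent window, with nothing to say that later cases had been reported. For a rare event, one or two uncounted cases can be the difference between none observed and a non-zero rate.

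There is a second, practical gap. Protocol 8.7 specifies the adverse event eCRF page only for events through 28 days after the last dose, while Protocol 8.9 has AESIs reported on a separate SAE/AESI form. Neither document says which source feeds the analysis of later AESIs.

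**Working it through.** The plan states no MDS/AML rate, so there is no figure to reproduce. The check is a reading of the rules together, followed by a scale calculation.

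**1. How a case is routed.** Treatment-emergent status depends on onset date (SAP 11.1). Protocol 8.7.1 dates onset from the start of the event or of the signs or symptoms tied to it.

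| First related signs | Reported? | Where SAP 11.1 puts it |
|---|---|---|
| First dose to last dose + 28 days | Yes | TEAE tables |
| Onset date missing in whole or part, timing cannot be determined | Yes | TEAE tables (missing-date rule) |
| More than 28 days after last dose | Yes, as an AESI | By-patient listing only |

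The third row is the gap.

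**2. Size of one case.** The denominator is the safety population (all dosed patients), planned at about 200. One case is 1/200 = 0.5 percentage points. Exact (Clopper-Pearson) 95% limits at N = 200:

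- 0/200: 0% (0 to 1.8%)
- 1/200: 0.5% (0.01 to 2.8%)
- 2/200: 1.0% (0.1 to 3.6%)

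**3. How many cases might be affected (assumed inputs).** Let r be the true cumulative MDS/AML rate and s the share of cases with onset after the window. Neither is in the documents. I took r = 0.5%, 1% and 2%, and s = 25%, 50% and 75%.

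- Expected cases in the TEAE tables = 200 × r × (1 − s)
- Expected cases omitted = 200 × r × s
- Chance of at least one omitted = 1 − (1 − r × s)^200

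| r | s | All cases | In TEAE tables | Omitted | Chance of ≥ 1 omitted |
|---|---|---|---|---|---|
| 0.5% | 25% | 1 | 0.75 | 0.25 | 22% |
| 0.5% | 50% | 1 | 0.50 | 0.50 | 39% |
| 0.5% | 75% | 1 | 0.25 | 0.75 | 53% |
| 1% | 25% | 2 | 1.5 | 0.5 | 39% |
| 1% | 50% | 2 | 1.0 | 1.0 | 63% |
| 1% | 75% | 2 | 0.5 | 1.5 | 78% |
| 2% | 25% | 4 | 3 | 1 | 63% |
| 2% | 50% | 4 | 2 | 2 | 87% |
| 2% | 75% | 4 | 1 | 3 | 95% |

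**4. Is that range of s reasonable?** As a rough guide, take time on drug as exponential with median 2 to 3 months (using the progression time in the protocol's synopsis rationale as a proxy), survival as exponential with median 6 to 9 months (the second-line figure in Protocol 1.1.2), and a constant MDS/AML hazard. Mean time to the end of the window is median/ln 2 + 28/30.4375 months, and mean survival is median/ln 2. The share of survival time after the window is 1 minus their ratio:

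- 2 and 6 months: 1 − 3.81/8.66 = 56%
- 2 and 9 months: 1 − 3.81/12.98 = 71%
- 3 and 6 months: 1 − 5.25/8.66 = 39%
- 3 and 9 months: 1 − 5.25/12.98 = 60%

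These shares lie inside the range used in step 3. They show that post-window time is not negligible. They do not predict a count.

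**The case against.** The strongest objection concerns the marrow work-up in Protocol 5.4.1.2. Its trigger reads "If, after 42 days of interruption of rucaparib, the anemia has not improved to CTCAE Grade" 1 or lower. Since 42 − 28 = 14, a reader might infer that any case found this way lies at least 14 days outside the window. The documents do not support that inference. Status depends on onset, not diagnosis, and Protocol 8.7.1 dates onset from the first related signs or symptoms. A case found through this work-up would normally be dated to the anemia that caused the hold, which is inside the window. The 42 days also count from an interruption, and if dosing resumes by agreement the window moves later. The work-up is therefore not evidence of omission.

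Three further points have weight:

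- SAP 11.1 describes its table list as not exhaustive, so an AESI table is not ruled out. That stands as far as it goes: such a table is allowed but not planned, and the sentence on non-TEAEs gives the opposite default.
- Late cases are not hidden. They are assigned to listings, and a handful could be counted by hand. True, but a hand count has no prespecified denominator, window or interval.
- Survival in this setting is short and the trial has about 200 patients, so late cases may be few or none. This limits the size of the problem but does not remove it.

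The sentence in Protocol 9.7.1 on collecting only treatment-emergent events might be read as meaning that later AESIs are lost. The repeated reporting rules elsewhere in the protocol, and the SAP's own provision for post-treatment events, show that it is a wording conflict.

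**Conclusion.** The point holds in a limited form. If the plan is followed as written, an MDS or AML case whose first signs begin more than 28 days after the last dose is reported but is absent from every adverse event table the SAP names. Each such case is worth 0.5 percentage points of about 200 patients. Under the assumed rates and late shares above, 0.25 to 3 cases would be expected to be omitted, and the chance of at least one runs from 22% to 95%. These figures rest wholly on those assumptions.

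Two stronger conclusions are not supported. A reader might infer that the trial's principal late-toxicity rate will be understated, but neither document defines such a rate; the gap is that no AESI incidence is planned at all. Nor is understatement certain: it needs at least one case with late onset. This is a reporting gap in the SAP that is cheap to close. It does not affect the efficacy analysis.

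**What to change.** 1. Add to SAP 11.1 a table of AESIs, with MDS and AML identified, from first dose to last contact in the safety population. Give number, percent and exact 95% confidence interval, split into onset up to last dose plus 28 days and onset after that.
2. Name the data source for AESIs after day 28, for example the SAE/AESI Report Form in Protocol 8.9, because Protocol 8.7 specifies the adverse event eCRF only through day 28.
3. In Protocol 9.7.1, change *collected* to *summarized* in the sentence on treatment-emergent events and except the AESI table, so that it agrees with Protocol 7.5.3, 7.6.4.1 and 8.7 to 8.9.

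The cost is one extra table, a sentence on data source and a wording correction. No new patient assessments are needed, since the protocol already requires these reports.

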11.2 Clinical Laboratory Evaluations

Clinical laboratory evaluations include the continuous variables for hematology, serum chemistry, and urinalysis. The laboratory values will generally be presented in International System (SI) units. The on-treatment period will be defined as the time from first dose to 28 days after the last dose of study drug. Laboratory values collected during the on-treatment period will be included in the summary tables. The laboratory values collected after the on-treatment period will only be presented in the data listings.

The summary of laboratory data will include shift tables based on CTCAE for shifts in grade from baseline to maximum, minimum, and last value during the on-treatment period.

The summary of laboratory data will include descriptive statistics (N, mean, StD, minimum, median, and maximum) of the maximum, minimum, and last value during the on-treatment period. Summaries using descriptive statistics of the change from baseline to the maximum, minimum, and last value during the on-treatment period will also be given.

Supporting laboratory data including normal ranges and abnormal laboratory flags will be provided using by-patient listings. Separate listings will be produced for clinically significant laboratory abnormalities (ie, those that meet Grade 3 or 4 criteria according to CTCAE).

11.3 Vital Signs

The on-treatment period will be defined as the time from first dose to 28 days after the last dose of study drug. Vital sign measurements collected during the on-treatment period will be included in the summary tables. The vital sign measurements collected after the on-treatment period will only be presented in the data listings.

The summary of vital sign data will include descriptive statistics (N, mean, StD, minimum, median, and maximum) of the maximum, minimum, and last value during the on-treatment period. Summaries using descriptive statistics (N, mean, StD, minimum, median, and maximum) of the change from baseline to the maximum, minimum, and last value during the on-treatment period will also be given. The data will be presented separately for each randomized treatment group and overall.

13 APPENDICES

Appendix 1 Response Evaluation Criteria in Solid Tumors

The RECIST guidelines (Version 1.1) are described in Eisenhauer (2009)⁵ and at <http://www.eortc.be/Recist/Default.htm>. A short summary is given below.

Measurable Disease:

Tumor lesions: measurable lesions are defined as those that can be accurately measured in at least 1 dimension (longest diameter to be recorded) with the following:

- A minimum size of 10 mm by CT scan (CT scan thickness no greater than 5 mm).
- A minimum size of 10 mm caliper measurement by clinical exam (lesions that cannot be accurately measured with calipers should be recorded as nonmeasurable).
- A minimum size of 20 mm by chest X-ray.

All tumor measurements must be recorded in millimeters (or decimal fractions of centimeters).

Malignant lymph nodes: to be considered pathologically enlarged and measurable, a lymph node must be ≥ 15 mm in short axis when assessed by CT scan (CT scan slice thickness recommended to be not greater than 5 mm). At baseline and in follow-up, only the short axis will be measured and followed.

Nonmeasurable Disease:

All other lesions (or sites of disease), including small lesions (longest diameter < 10 mm or pathological lymph nodes with ≥ 10 to < 15 mm short axis), as well as truly nonmeasurable lesions, are considered nonmeasurable disease. Lesions considered truly nonmeasurable include leptomeningeal disease, ascites, pleural/pericardial effusions, inflammatory breast disease, lymphangitic involvement of skin and lung, and abdominal masses/abdominal organomegaly identified by physical exam that is not measurable by reproducible imaging techniques.

Bone Lesions

Bone lesions, cystic lesion, and lesions previously treated with local therapy require particular comment. Bone scan, PET scan, or plain films are not considered adequate imaging techniques to measure bone lesions. However, these techniques can be used to confirm the presence or disappearance of bone lesions.

Lytic bone lesions or mixed lytic–blastic lesions with identifiable soft tissue components that can be evaluated by cross-sectional imaging techniques such as CT or MRI can be considered as measurable lesions if the soft tissue component meets the definition of measurability described above.

Blastic bone lesions are nonmeasurable.

Cystic Lesions

Lesions that meet the criteria for radiographically defined simple cysts should not be considered as malignant lesions (neither measurable nor nonmeasurable) because they are, by definition, simple cysts.

Cystic lesions thought to represent cystic metastases can be considered as measurable lesions if they meet the definition of measurability described above. However, if noncystic lesions are present in the same patient, these are preferred as target lesions.

Lesions with Prior Local Treatment

Tumor lesions situated in a previous irradiated area or in an area subjected to other locoregional therapy are usually not considered measurable unless there has been demonstrated progression in the lesion.

Target Lesions

All measurable lesions up to a maximum of 2 lesions per organ and 5 lesions in total, representative of all involved organs, should be identified as target lesions and recorded and measured at baseline. Target lesions should be selected on the basis of their size (lesions with the longest diameter) and their suitability for accurate repeated measurements (either by imaging techniques or clinically). A sum of the longest diameter (LD) for all target lesions will be calculated and reported as the baseline sum LD. The baseline sum LD will be used as reference by which to characterize the objective tumor response.

Nontarget Lesions

RECIST criteria require unequivocal quantification of the changes in tumor size for adequate interpretation of the sum of target lesions. Consequently, when the boundaries of the primary are difficult to delineate, this tumor should not be considered a target lesion.

Guidelines for Evaluation of Measurable Disease

The same method of assessment and the same technique should be used to characterize each identified and reported lesion at baseline and during follow-up. Imaging-based evaluation is preferred to evaluation by clinical examination when both methods have been used to assess the antitumor effect of a treatment.

Evaluation of Target Lesions	
Complete Response	Disappearance of all target lesions. Any pathological lymph nodes (whether target or nontarget) must have reduction in short axis to < 10 mm.
Partial Response	At least a 30% decrease in the sum of the LD of target lesions, taking as reference the baseline sum LD.
Stable Disease	Neither sufficient shrinkage to qualify for partial response nor sufficient increase to qualify for PD, taking as reference the smallest sum LD since the treatment started.
Progressive Disease	At least a 20% increase in the sum of the LD of target lesions, taking as reference the smallest sum on study (this includes the baseline sum if that is the smallest on study). In addition to the relative increase of 20%, the sum must also demonstrate an absolute increase of at least 5 mm. The appearance of one or more new lesions is also considered progression.

Abbreviations: LD = longest diameter; PD = progressive disease.

Evaluation of Nontarget Lesions	
Complete Response	Disappearance of all nontarget lesions and normalization of tumor marker level.
Stable Disease/Incomplete Response	Persistence of 1 or more nontarget lesion(s) or/and maintenance of tumor marker level above the normal limits.
Progressive Disease	Appearance of 1 or more new lesions and/or unequivocal progression of existing nontarget lesions.

If tumor markers are initially above the institutional ULN, they must normalize for a patient to be considered a complete responder.

Evaluation of Best Overall Response

The best overall response is the best response recorded from the start of the treatment until disease progression/recurrence (taking as reference for PD the smallest measurements recorded since the treatment started). The patient's best response assignment will depend on the achievement of both measurement and confirmation criteria.

Evaluation of Best Overall Response			
Target Lesions	Nontarget Lesions	New Lesions	Overall Response
CR	CR	No	CR
CR	Non-CR/non-PD	No	PR
CR	Not evaluated	No	PR

Evaluation of Best Overall Response				
Target Lesions		Nontarget Lesions	New Lesions	Overall Response
PR		Non-PD or not evaluated	No	PR
SD		Non-PD or not evaluated	No	SD
Not Evaluated		Non-PD	No	NE
PD		Any	Yes or No	PD
Any		PD	Yes or No	PD
Any		Any	Yes	PD
CR	=	complete response		
NE	=	not evaluable.		
PD	=	progressive disease		
PR	=	partial response		
SD	=	stable disease		

Patients with a global deterioration of health status requiring discontinuation of treatment without objective evidence of disease progression at that time should be classified as having symptomatic deterioration. Every effort should be made to document the objective progression, even after discontinuation of treatment.

In some circumstances, it may be difficult to distinguish residual disease from normal tissue. When the evaluation of CR depends on this determination, it is recommended that the residual lesion be investigated (fine needle aspiration/biopsy) prior to confirming the complete response status.

Confirmatory Measurement/Duration of Response

Confirmation

If a complete response (CR) or partial response (PR) is noted, confirmatory scans should be performed at least 4 weeks after response was first documented.

Duration of Overall Response

The duration of overall response is measured from the time measurement criteria are met for CR or PR (whichever is first recorded) until the first date that recurrent or PD is objectively documented (taking as reference for PD the smallest measurements recorded since the treatment started).

The duration of overall CR is measured from the time measurement criteria are first met for CR until the first date that recurrent disease is objectively documented.

Duration of Stable Disease

Stable disease (SD) is measured from the start of the treatment until the criteria for progression are met, taking as reference the smallest measurements recorded since the treatment started.

